***(All advertising must be submitted for review in its final printed/recorded form)**

Note: Attach copies of ALL recruitment materials in the attachment Section

Flyers/posters

Email

Is there any possibility that potential participants may feel coerced to participate?

No

Is there any possibility that potential participants may feel undue influence to participate?

No

Participant Compensation/Costs

Will participants be compensated?

Yes

Form of Compensation

Cash or Check

What is the approximate monetary value?

\$100

Describe the remuneration plan.

Participants will not receive remuneration for Sessions 1-3. Participants will be paid \$40 on completion of Session 4, and \$60 on completion of Session 5. Typically, the information provided from Session 1 is a motivational factor for participants who are habitual exercisers. An equivalent "fitness assessment" might cost \$200-300, or more. Sessions 2 and 3 are essentially supervised workouts.

Will a 1099 be issued?

No

Will participants incur any costs to participate in this research?

Yes

Explain. This should be clearly outlined in the consent form.

To remain compliant with state law and university regulations, study participants must purchase their own marijuana. The typical price for Ripple Blood Orange Gummies is \$18-20 for 20 gummies. The product is sold in units of multiple servings. This is clearly outlined in the consent form.

Risks and Benefits

Minimal risk "means that the probability and magnitude of harm or discomfort anticipated in the research are not greater in and of themselves than those ordinarily encountered in daily life or during the performance of routine physical or psychological examinations or tests." [Department of Health and Human Services 45 CFR 46.102(j)]

Please indicate the researchers' evaluation of the overall risk level, and describe all known risks or discomforts associated with the study procedures, as prompted below. Note that any risks identified here should be consistent with risks you will disclose to participants in the consent process.

Greater than Minimal Risk

Are there risks associated with physical well-being?

Yes

Please describe.

Venous Blood Sampling Minor discomfort of having the needle inserted and taped to an hand/wrist. In about 1 in 10 cases, a small amount of bleeding will occur under the skin that will cause a bruise. The risk of forming a blood clot in the vein is about 1 in 100, and the risk of significant blood loss is 1 in 1,000. Body Composition The risks associated with the DEXA are very low. The maximum radiation dose subjects will receive in this study is less than 1/3000th of the federal and state occupational whole body dose limit allowed to radiation workers. Put another way, subjects will receive less than 1.3 mrem from this scan and they already receive approximately 450 mrem /year from normal background radiation dose in Colorado. The more radiation one receive over the course of one's life, the more the risk increases of developing a fatal cancer or inducing changes in genes. The radiation dose subjects receive from this scan is not expected to significantly increase these risks, but the exact increase in such risks is not known. There are no discomforts associated with this procedure. Women who are or could be pregnant should receive no unnecessary radiation and should not participate in this study.

Exercise Stress Test, Time-Trial and Wingate Test There is a very small chance of an irregular heartbeat during exercise (< 1% of all subjects). Other rare risks of a stress test are heart attack (< 5 in 10,000) and death (<2 in 10,000). Wearing a mouthpiece and nose-clip can sometimes cause dryness in the mouth and mild discomfort. Exercise can make people feel very tired. Very difficult exercise might make people feel dizzy or queasy; people may faint or vomit. Further, very difficult exercise performed by people who don't usually exercise is likely to induce considerable muscle soreness and increase the risk of minor musculoskeletal injuries (sprains and strains).

Ingestion of Edible Cannabis (From WebMD and Drugs.com) (also see "Psychological Well-Being) Cannabis might cause fast heartbeat and high blood pressure. It might also increase the risk of a having heart attack. Certain chemicals in cannabis can weaken the immune system. This might make it more difficult for the body to fight infections. Cannabis might increase the risk of an allergic reaction in people with allergies to foods like tomatoes, bananas, and citrus fruit. It is unclear if cannabis worsens chronic liver disease. While some weak evidence suggests that there might be a link, other evidence has not found a link. Using cannabis after having a stroke might increase the risk of having a second stroke. Cannabis affects the central nervous system or the brain and nerves. It might slow the central

nervous system too much when combined with anesthesia and other medications during and after surgery.

Are there risks associated with psychological well-being?

Yes

Please describe.

Ingestion of Edible Cannabis (From WebMD and Drugs.com) (also see "Physical Well-Being) Use of cannabis is likely to lead to an altered state of consciousness. The user may feel "high", very happy, euphoric, relaxed, sociable and uninhibited. The user may experience distorted perceptions of time and space. The user may feel more sensitive to things around them, and may also experience a more vivid sense of taste, sight, smell and hearing. Using cannabis might make manic symptoms worse in people with bipolar disorder. Cannabis use, especially frequent use, might increase the chance of getting depression. It can also worsen symptoms of depression and increase thoughts about suicide in those that already have depression. Using cannabis might make symptoms of schizophrenia worse.

Are there risks associated with economic well-being, including employability?

Yes

Please describe.

Participants wishing to seek/maintain employment with institutes that frequently perform drug testing should not participate. Given that the participants will all be habitual users of cannabis, this risk is low and the situation unlikely.

Are there risks associated with social well-being, including reputational risks?

No

Describe how the benefits of the research justify the likely risks to participants.

The use of cannabis by athletes is widespread. Many athletes believe cannabis may improve their performance during training and competition. There are no up-to-date data to support these beliefs. Our study will inform athletes and others considering cannabis use in conjunction with exercise of the actual effects and determine whether cannabis/marijuana is ergogenic (less likely) or ergolytic (more likely).

Describe direct research benefits to the participants, if any.

If the participants fall into the category of athletes/exercisers who use cannabis prior to and/or during exercise, they will learn if/how it affects their performance and their physiological response to exercise.

Describe the indirect research benefits to society.

Our study will address a knowledge gap identified by several independent scientific groups; thus the proposed project is a response to recommendations for future research. The general public may benefit from the ability to make informed decisions as to the interaction between exercise and cannabis.

Data Management

Data management plans, including plans for data sharing, are integral to project development. How you decide to collect, store, share and/or destroy data impacts your consent process, research procedures, data analysis, and publication.

Responses in this section constitute your plan. For guidance on how to answer these questions and plan for the data lifecycle, reference the resources and tools listed here.

[Data Management Services at CSU Libraries](#)

[General guidance and unfunded projects](#) (DMPTool)

[Funder-specific guidance and templates](#) (DMPTool)

If you choose to create a standalone data management plan (DMP) for your own purposes or at the direction of a funding agency, please attach that document to your protocol, also.

A [DMP fillable template](#) is available from CSU Libraries.

How will the data be stored and backed up during the research?

As per advice provided by the IRB during previous protocol reviews, we will employ the 3-2-1 approach to data management. Specifically, our data are stored on a password protected PC within the lab, on a secure on-campus server maintained (and backed up) by our college, and on a secure external (off-campus) server (OneDrive). The data are typically stored as an Excel file, but also as a csv file (i.e. in a format not dependent on the availability of a specific platform (OS) or software edition.

The default process for gaining consent is to use a signed form. Knowing that this does not always make sense, the IRB can approve alterations to what information is included, waive the requirement to get a signature or waive the requirement to obtain consent altogether when the request meets specific criteria.

Follow the prompts below to describe all consent processes and provide justification for any requested alterations or waivers.

Will informed consent be obtained from all research subjects (and/or their parents or legally authorized representatives)?

Yes

CSU Consent Personnel

[name]

[name]

[name]

[name]

[name]

No

Are you requesting a waiver of documentation of consent?

No

Consent

You do not have any procedures that include deception. If you are going to deceive or incompletely inform any subjects about any aspect of this study describe in the procedures section.

List each consent process

Who will obtain subjects consent?

Personnel

[name]

Personnel

[name]

Personnel

[name]

Personnel

[name]

Personnel

[name]

Which participant group is this consent process for?

All participants.

How is consent being obtained?

Whenever possible, participants are provided with a copy of the informed consent in advance (usually via email) for review at their convenience.

During the actual in-person consent process, research team members review the form line-by-line, ask the participant questions to ascertain correct comprehension, answer questions posed by the participant, and obtain written signatures.

Will non-English speaking participants be enrolled?

No

Non-English speaking participants will be unable to provide informed consent.

Are any subjects unable to legally provide consent?

No

Conflict of Interests

For guidance on how to answer these questions and information please visit the [CSU Conflict of Interest page](#).

Does the research involve a drug, device, or biological invented by you, an immediate family member or other Research Personnel?

No

Is the research sponsored by an entity with which you, an immediate family member, or other Research Personnel have a paid consulting or advising relationship?

No

Will you, members of your immediate family, or other Research Personnel receive special compensation or increased compensation if the research generates a favorable outcome?

No

Will you, members of your immediate family, or other Research Personnel receive any money, gift or anything of monetary value above and beyond the actual costs of enrollment, conduct of the research, and reporting on the results, including, but not limited to, finders fees, referral fees, recruitment bonuses, and an enrollment bonus for reaching an accrual goal or similar types of payments?

No

Do you, members of your immediate family or other Research Personnel have any other interests or relationships (including volunteer services) that might constitute a conflict of interest or an appearance of conflict of interest in connection with the research project?

No

Will the payment you receive for services provided during the conduct of the research (e.g., investigator and Research Personnel time and tests) be inconsistent with fair market value for those services?

No

Significant Financial Interest: Please check Yes or No for each item below.

Will you, your immediate family members or other Research Personnel receive salaries, royalties and/or other payments for services (e.g., consulting fees, honoraria, research design, management position, independent contractor, service on advisory or review committees, board membership seminars, lectures or teaching engagements when totaled together exceeded \$5,000 during the previous 12 months or are expected to exceed \$5,000 over the next 12 months)? This excludes reasonable costs of conducting the research, as specified in the research agreement.

No

Do you, your immediate family members, or other Research Personnel hold any ownership interests including stocks, bonds, or stock options that exceed \$5,000 and/or that constitute more than a five percent (5%) ownership interest in the sponsoring organization? This does not include any interests held solely by reason of investment in a business by a mutual, pension or other institutional investment fund over which the investigator and/or his or her immediate family do not exercise day-to-day control of investment decisions.

No

Minimizing Risks and Disclosure to Subjects

Have you disclosed any actual, potential or perceived conflicts of interest in the consent form? Research Personnel are required to disclose all such conflicts to all research participants in the research consent form.

No

By submitting this form, you are attesting that you have read [Colorado State University's policy on Conflict of Interest](#) and agree to abide by its terms. You will update this disclosure form when new or changes in conflict of interest arise, and that you will comply with any conflict management plan required by the Institutional Review Board (IRB) to manage, reduce, or eliminate any actual or potential conflict of interest for the duration of the research.

Attachments

Attach all relevant documentation to your research in this section. Please label each item appropriately, so your IRB reviewers understand the purpose and population each document aims to address. Please delete the existing attachment and upload the Tracked Changes version and Clean revised document for review to update or revise any existing attachments.

Any documentation that a participant will see must be reviewed and approved by the IRB, including consent, recruitment, communications, tools, instruments, etc. Additional documents required for review include funding proposals, contracts, letters of agreement, methodology, related approvals, etc. For more information and guidance on what documentation to attach, please visit the IRB website.

Answers within your application indicate that the following documentation is required:

Attachment Type

Other

Attachment

[CANNABIS ATHLETIC PERFORMANCE.PDF](#)

Name

Cannabis and Athletic Performance

Attachment Type

Other

Attachment

[CANNABIS EXERCISE PERFORMANCE GATORADE.PDF](#)

Name

Cannabis and Exercise Performance

Attachment Type

Other

Attachment

[ACUTE EFFECTS OF MARIHUANA SMOKING ON MAXIMAL EXERCISE PERFORMANCE.PDF](#)

Name

Marijuana and Maximal Exercise

Attachment Type

Other

Attachment

[PHARMACOKINETIC INVESTIGATION OF COMMERCIALLY AVAILABLE EDIBLE MARIJUANA.PDF](#)

Name

PK Edible Marijuana - CSU Study

Attachment Type

Recruitment Materials

Attachment

[2827 RECRUITMENT FLYER.DOCX](#)

Name

Recruitment Flyer

Attachment Type

Recruitment Materials

Attachment

[2827 RECRUITMENT EMAIL.DOCX](#)

Name

Recruitment email

Attachment Type

Screening Tool or Procedure

Attachment

[2827 SCREENING FORM 10072021.DOCX](#)

Name

2827 Screening Form

Attachment Type

Other

Attachment

[CANNABIS USE AND SPORT.PDF](#)

Name

Cannabis Use and Sport

Attachment Type

Consent

## Statistical Analysis Plan

All data, unless otherwise stated, are expressed as mean and standard deviation. To compare baseline values between placebo and edible marijuana for circulating concentrations of THC, and THC metabolites, one-way analysis of variance (placebo vs edible marijuana) was used, unless a non-parametric equivalent (i.e. one way analysis of variance on ranks) was required on account of unequal variance. The standardized exercise statistical analysis was conducted in R (R Core Team; Vienna, Austria) as linear mixed models using the Lmer and LmerTest packages (Bates et al., 2015), and Emmeans package was used for post hoc Tukey testing to explore main effects and interactions. Time and Condition were considered fixed effects, whereas Subject was considered a random effect to account for the repeated measures. Unlike an electrically braked ergometer, it is not feasible to externally fix the work rate on an air braked ergometer; the actual work rate is determined by the damper setting and the participant's pedal cadence. During the standardized exercise test, participants were instructed to exercise at 50, 100 and 150 W. Accordingly, for statistical analysis of these data, work rate error, defined as the difference between the prescribed work rate and the actual work rate, was considered as a covariate in our model. One- and two-way analysis of variance, with repeated measures, were employed to detect differences among variables during the performance of the FTP20 and in the sprint to fatigue tests using SigmaPlot 14.5 (Systat Software Inc., San Jose, California). Specifically, one-way repeated measures ANOVA was used to compare mean work rate (placebo vs edible marijuana). Two-way ANOVA with repeated measures (time) was used to compare power outputs across consecutive stages (placebo vs edible marijuana). One-way repeated measures ANOVA was used to compare mean power, peak power, time to fatigue, and total work done (placebo vs edible marijuana) during the sprint to fatigue tests. Significance was defined as  $p < 0.05$ . Wherever a significant difference was detected, a post-hoc Tukey test was utilized to further explore these differences.

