Official Title: Influence of Edible Marijuana on Endurance Exercise Performance

NCT Number: NCT05192239, Unique Protocol ID: 2827

Document Date: 12/31/2022

#2827 - Influence of edible marijuana on endurance exercise performance

Protocol Information

Submission Type	Review Type	Status	Time in Current Status
Close Request	--	Closed	Since January 3 – 6 months
Initial Approval Date	Initial Review Type		
Nov 30, 2021	Full Board		

Close Comment

Thank you for informing the IRB that the work associated with this protocol is complete. To comply with federal regulations, please be sure to securely keep all research records, including signed informed consent documents, for a period of 3 years from this date.

Let us know if you have any questions.

[contact]

Feedback

Protocol Close Request Form

Close Request

Completed Date

December 31, 1969

Summary of Findings

A manuscript was accepted for publication in the journal, *Frontiers In Physiology*. Here is the title and abstract: **Edible marijuana and cycle ergometer exercise**

Purpose: There is extensive public and scientific interest in the influence of cannabis and the psychoactive cannabinoid, delta-9-tetrahydrocannabinol (THC), on exercise performance. Unfortunately, recent, up-to-date studies are lacking. The aim of the current study was to address the hypothesis that ingestion of edible marijuana, prior to exercise, would have unfavorable effects on the physiological response to exercise and on exercise performance.

Methods: 17 Healthy adult male and female habitual exercisers, who were regular users of cannabis products, were screened for study participation. 10 were enrolled, and data from 9 [8 males, 1 female, aged 25 ± 3 years, with peak oxygen uptake of 56.5 ± 11.7 ml/kg/min (mean \pm SD)] were retained. Participation included two exercise sessions, each preceded by self-administration and ingestion of either edible marijuana (containing 10 mg THC) or placebo. Cardio-respiratory responses (via indirect calorimetry) to stationary cycle ergometer exercise (8 min at 50, 100 and 150 W) were recorded before completion of a 20-min Functional Threshold Power test (FTP20) and a sprint test involving maximal effort until volitional fatigue.

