Results: Edible marijuana increased the concentration of circulating THC and THC metabolites, and evoked sensations of intoxication and altered psychoactive state. Cardio-respiratory responses to staged cycle ergometer exercise were normal and were unaffected by edible marijuana. Compared with placebo, edible marijuana did not influence FTP20 (Placebo 253 ± 75 vs THC: 251 ± 72 W (mean \pm SD); $p > 0.45$) or peak power output during the sprint test (Placebo: 710 ± 201 vs. THC: 732 ± 136 W; $p = 0.864$). **Conclusion:** 10 mg of THC, when ingested prior to exercise by regular exercisers and habitual users of cannabis, had little effect on the physiological response to standardized cycle ergometer exercise, and was neither ergogenic nor ergolytic. The manuscript is available here: <https://pubmed.ncbi.nlm.nih.gov/36545283/>

In the box below, please attach any relevant publications that resulted from the data collection for this study, and/or any other relevant documentation that should be kept with this file.

Close Request Questions

Completed As Planned?

Yes

Please state the number of participants enrolled in this study.

17

Please state the number of participants who completed this study.

10

Please state the number of participants who withdrew from this study.

7

Were there any unanticipated problems or adverse events that were *not previously* reported to the IRB?

No

General Information

Principal Investigator

[name]

Lead Unit

Health + Exercise Science (CO-1582)

Title

Influence of edible marijuana on endurance exercise performance

People**People****Person**

[name]

Home Unit

Health + Exercise Science (CO-1582)

Email Address

[contact]

Phone**CSU Status****Researcher Role**

Principal Investigator

Contact Roles

Admin

Permissions

Full Access

People Attachments

Person

[name]

Home Unit

Health + Exercise Science (CO-1582)

Email Address

[contact]

[contact]

CSU Status

Other

Researcher Role

Key Person

Contact Roles

Permissions

Full Access

People Attachments

Person

[name]

Home Unit

Health + Exercise Science (CO-1582)

Email Address

[contact]

Phone**CSU Status****Other****Researcher Role**

Key Person

Contact Roles**Permissions**

Full Access

People Attachments**Person**

[name]

Home Unit

Health + Exercise Science (CO-1582)

Email Address

[contact]

[contact]

CSU Status

Other

Researcher Role

Key Person

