The purpose of the proposed project is to provide athletes and the scientific community with data pertaining to the acute influence of edible marijuana on exercise performance, and the physiological responses to standardized exercise. Specifically, we wish to determine: 1. The influence of edible marijuana on cardio-respiratory and metabolic responses to standardized cycle ergometer exercise. 2. The influence of edible marijuana on endurance exercise (time-trial) performance.

What do the investigators hope to learn from the project?

We wish to determine if edible marijuana, ingested prior to exercise, is ergogenic (improves performance) or ergolytic (decreases performance). We hypothesize that edible marijuana will be ergolytic.

Describe how sharing results of this study could influence behavior, practice, theory, future research designs. Specifically, how will study results apply to a larger population than the studied participants?

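### The standardized-exercise mixed model names Subject as its only random effect, so Condition and Time-by-Condition share one error term that does not match the crossover; the baseline THC test is worded as unpaired

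*SAP*

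**What the plan says.** The SAP (Statistical Analysis Plan, a single section) analyses the 50, 100 and 150 W stages with linear mixed models in R: "Time and Condition were considered fixed effects, whereas Subject was considered a random effect to account for the repeated measures". Work-rate error enters as a covariate. Follow-up is described as "Emmeans package was used for post hoc Tukey testing to explore main effects and interactions", so the Time-by-Condition interaction is among the effects examined. No formula is given, and no session term, random slope or residual correlation structure is mentioned.

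For THC and metabolites at baseline, the SAP says "one-way analysis of variance (placebo vs edible marijuana) was used, unless a non-parametric equivalent" (ANOVA on ranks) "was required on account of unequal variance". In the same paragraph the time-trial comparison is worded differently: "one-way repeated measures ANOVA was used to compare mean work rate (placebo vs edible marijuana").

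The Protocol (Procedures, Sessions 2 to 5) describes a randomized crossover with one session per condition, at least 5 days apart, and three 8-minute stages in each session. The first aim in Summary and Purpose is "The influence of edible marijuana on cardio-respiratory and metabolic responses to standardized cycle ergometer exercise", and this mixed model is the only analysis planned for it. The Summary of Findings reports: "Cardio-respiratory responses to staged cycle ergometer exercise were normal and were unaffected by edible marijuana".

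**The concern.** A Subject intercept allows for some people running higher than others overall. It does not allow for two further sources of variation:

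- **Session (Subject-by-Condition).** All three stages of a session share that day's state, and each condition is given on one day only. Condition must therefore be judged against session-to-session variation.
- **Subject-by-Time.** People differ in how steeply they respond to rising load. The loads are fixed, while the Summary of Findings describes participants "with peak oxygen uptake of 56.5 ± 11.7 ml/kg/min", so a given wattage is a different relative intensity for different people. Some variance of this kind is plausible.

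If both are left in one residual, neither test has the right yardstick. A significant Condition effect could be spurious, and a non-significant interaction could simply reflect an inflated error term.

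The baseline test raises a separate point. A plain one-way ANOVA treats two samples from the same nine people as two independent groups. If a person's two values are correlated, a real carry-over of residual THC is more likely to be missed.

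**Working it through.** The documents give no power or error-rate figure for these analyses, so there is none to reproduce.

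**Inputs.** n = 9 analysed (Protocol, Summary of Findings); 2 conditions; 3 stages (Protocol, Procedures); 5% significance (SAP). One Time value per stage is assumed, since the SAP does not define the levels of Time. Let q be the Subject-by-Condition variance and s the Subject-by-Time variance, each divided by the residual variance. Neither is in the documents, so ranges are shown.

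**Degrees of freedom.** There are 9 × 2 × 3 = 54 observations. The Subject-only residual has 54 − 6 cells − 8 subjects = 40. It splits as follows:

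| Component | df | Expected mean square |
|---|---|---|
| Subject-by-Condition | 8 | 1 + 3q |
| Subject-by-Time | 16 | 1 + 2s |
| Remainder | 16 | 1 |

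The pooled residual has expectation [8(1 + 3q) + 16(1 + 2s) + 16]/40 = 1 + 0.6q + 0.8s. Condition should be compared with 1 + 3q, and the interaction with 1.

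**Direction.** For Condition the pooled term is too small when 0.6q + 0.8s < 3q, that is s < 3q (p-values too small), and too large when s > 3q. For the interaction it is too large whenever q or s exceeds zero. The ratio of model to true standard error for Condition is √[(1 + 0.6q + 0.8s)/(1 + 3q)]. At q = 0.25 this is √(1.15/1.75) = 81% for s = 0, √(1.75/1.75) = 100% for s = 0.75, and √(2.75/1.75) = 125% for s = 2.

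**Size.** 40,000 simulated data sets per setting, no true effect, no covariate. Percentage of Condition tests rejecting, Subject-only model (– = not listed):

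| q | s = 0 | s = 0.5 | s = 1 | s = 2 |
|---|---|---|---|---|
| 0 | 5.0 | – | 1.0 | – |
| 0.25 | 11.1 | 6.5 | 4.0 | 1.7 |
| 0.5 | 15.4 | 10.5 | 7.2 | 3.8 |
| 1 | 21.3 | – | 12.8 | 7.9 |

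At q = 0.25, s = 0.75, where s = 3q, the rate is 5.2%.

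Time-by-Condition, Subject-only model: at q = 0.25, 3.4% (s = 0) and 0.5% (s = 1); at q = 0.5, 2.3%, 0.8%, 0.3% and 0.1% for s = 0, 0.5, 1 and 2.

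Separate error terms, F(1,8) and F(2,16), reject 4.8–5.3% for both tests at all 20 settings examined. A larger sample does not cure the problem: at 30 participants, the Protocol's anticipated total, Condition rejects 15.6% at q = 0.5, s = 0 (20,000 runs).

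**Power, Subject-only against separate error terms.**

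| Effect | q, s | Subject-only | Separate |
|---|---|---|---|
| Interaction (0, 0.75, 1.5 residual SD by stage) | 0, 0 | 48% | 44% |
| same | 0.25, 1 | 16% | 43% |
| same | 0.5, 1 | 14% | 44% |
| Condition, 0.8 residual SD | 0.25, 2 | 39% | 49% |
| same | 0.1, 2 | 40% | 62% |

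**Covariate.** With a work-rate-error covariate unrelated to session state (half its variance between sessions, slope 0.5, both assumed; 6,000 runs), Subject-only Condition rejection is 10.8%, 15.0%, 6.8% and 1.4% at (q, s) = (0.25, 0), (0.5, 0), (0.5, 1) and (0.25, 2). If the covariate absorbs session variance, read q as what remains.

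**Baseline THC.** With correlation r between a person's two values, the unpaired standard error is too large by 1/√(1 − r), which is 1.41 at r = 0.5. For n = 9 and a 1-SD difference, unpaired against paired:

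| r | Type I error | Power |
|---|---|---|
| 0.3 | 2.2% vs 5.0% | 52% vs 61% |
| 0.5 | 1.0% vs 5.1% | 52% vs 75% |
| 0.8 | 0.1% vs 5.0% | 55% vs 98% |

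Rank versions at r = 0.5 have power 50% against 67%. At r = 0, pairing costs a little: 47% paired against 52% unpaired.

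**The case against.** The SAP wording is narrative, and without a formula the fitted model may have held more terms than it names. If so, the fault is one of reporting. That possibility stands, and the fix allows for it.

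The pooled error is valid when q = s = 0 and is close to nominal for Condition along s = 3q. Habituation sessions, a matched time of day, a standard meal and abstention may keep q small, and the covariate may remove part of it. This also stands: the direction for Condition is unknown. It does not rescue the interaction test, which is conservative whenever either variance is above zero.

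One Time value per stage is a reading of the design. More levels would change the figures but not the fault.

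The reported result was null, so no false positive entered the conclusions. At n = 9 even the correct interaction test has only 43–44% power here, so a null interaction would be weak evidence under either model. Pooling makes it weaker, down to about 15%.

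The missing repeated-measures wording for baseline THC may be loose drafting. But a switch to ranks for unequal variance belongs to an independent-groups test, which supports the unpaired reading.

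**Conclusion.** The concern holds for the analysis as described and should be fixed. One residual on 40 df serves two tests that need 8 and 16. Across the assumed variances, the nominal 5% Condition test rejects between 1.0% and 21.3% of the time. The interaction test falls below 1% in several settings, with a loss of power from about 43% to about 15%. These figures rest on assumed q and s, a balanced layout and one value per stage.

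The reported null for Condition is not overturned by this. A significant Condition effect from this model would be unreliable when s < 3q, and a non-significant interaction says little when q or s is above zero.

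The baseline point is smaller. It affects only the comparison between conditions, through an assumed r, and leaves the check of each participant's abstention untouched. Confidence is medium, because the fitted formula is not shown.

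**What to change.** **Mixed model.** State the formula and the levels of Time in the SAP. Fit `outcome ~ Time*Condition + work-rate error + (1|Subject) + (1|Subject:Condition) + (1|Subject:Time)` with Satterthwaite or Kenward-Roger degrees of freedom, and re-run on the existing data. Adding Subject-by-Condition alone is not enough: the interaction then rejects only 0.5% at q = 0.5, s = 1. If the fit is singular, do not revert to the Subject-only model. Report alongside it a two-way repeated measures ANOVA with both factors within subject (8 and 16 df, without the covariate). If both extra terms were already fitted, stating the formula is enough.

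**Baseline THC.** Use a paired test: one-way repeated measures ANOVA, or Wilcoxon signed-rank if the differences are clearly non-normal. Drop the unequal-variance trigger, since a paired test works on differences.

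**Cost.** SAP wording and a re-run. If both variances are truly zero, power for a Condition effect of 0.8 residual SD falls from 82% to 73%. Singular fits will be common: session variance is estimated as zero in 47% of runs at q = s = 0, 17% at q = 0.25, s = 0, and 9% at q = 0.5, s = 1. When s is truly zero, the three-term model rejects the interaction slightly too often (6.3–7.1%; up to 8.1% with the covariate, from 1,200 runs), which is why the ANOVA check is included.
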